1. BACKGROUND

Patients diagnosed with myeloproliferative neoplasms (MPNs)—including primary myelofibrosis (MF), essential thrombocythemia (ET), and polycythemia vera (PV)—face progressive bone marrow diseases largely driven by JAK2, CALR, or MPL mutations.¹⁻⁴ These conditions lead to overproduction of mature blood elements, marrow fibrosis, and heightened risks of thrombosis, cardiovascular events, and inflammatory complications.⁵⁻⁷ Although some patients live decades post-diagnosis, quality of life is often significantly reduced, and transformation to acute leukemia (MPN-BP) carries poor outcomes.⁸⁻⁹

Despite affecting an estimated 300,000 individuals in the U.S.,¹⁰ much remains unknown about the biological drivers of disease progression, predictive biomarkers, and meaningful surrogate endpoints. Existing MPN registries have provided valuable but limited insights, often constrained to single-center, clinician-reported, or trial-based cohorts.¹¹ This Registry addresses these gaps by integrating electronic medical records (EMRs), patient-reported outcomes (PROs), claims data, and genomic profiles across a broad patient spectrum—including pre-fibrotic MF (pre-PMF), MPN-AP, MPN-BP, or post-MPN AML, and MDS/MPN overlap syndrome (defined as CMML, MDS/MPN-SF3B1-T, MDS/MPN with neutrophilia, or MDS/MPN not otherwise specified), including patients originally diagnosed with one of these conditions but who have received one or more SCTs and/or BMTs—supporting comprehensive longitudinal tracking of disease evolution, treatment response, and EMR.

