3. OVERALL STUDY DESIGN

This is a prospective, non-interventional observational study, designed to evaluate patients with MPNs using both historical and prospective data. Participants will be enrolled over a minimum of three years during the initial run-in phase and followed longitudinally for disease progression, treatment response, clinical outcomes, and survival until withdrawal from the registry or death. Some participants may be followed for over ten years.

The study uses a multimodal data collection strategy, integrating:

- **EMRs:** Structured data extractions, including laboratory results, imaging, clinical notes, and treatment history.
- **PROs:** Longitudinal assessments of symptoms, quality of life, and functional status.
- **Medical Claims and Insurance Data:** Real-world healthcare utilization, treatment adherence, and cost metrics.
- **Mortality Data:** Vital status and cause-specific mortality obtained through national mortality dataset linkages, ensuring accurate survival analyses and minimizing loss to follow-up.
- **Affiliated Registries:** Select collaborations (e.g., CIBMTR, NCDB, SEER) may be used for external validation and cross-registry comparisons, though integration with international registries such as the European LeukemiaNet (ELN) will be considered only after addressing jurisdictional and data governance factors.

In addition to evaluating disease and treatment outcomes, the Registry will systematically monitor enrollment feasibility, participant retention, and heterogeneity across demographic, clinical, and geographic dimensions. These metrics will support reporting obligations to federal registries (e.g., ClinicalTrials.gov) and inform future feasibility assessments for interventional trials.

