4. OBJECTIVES

4.1. Primary Objectives

Stage 1: Feasibility Phase

The study will begin with a 12- to 24-month feasibility phase focused on participant retention, data completeness, EMR integration, and engagement strategies. Results from this phase will help optimize study operations, guide participant engagement, and inform potential protocol amendments.

- Evaluate enrollment feasibility and participant characteristics during the first 12–24 months.
- Characterize participant demographics, geographic distribution, and clinical settings.
- Assess inclusion of underrepresented populations to enhance the generalizability and heterogeneity of RWD.
- Assess representativeness of enrolled participants relative to the broader U.S. MPN population, ensuring alignment with clinical and demographic patterns.
- Determine the proportion of participants providing a Minimal Viable Dataset (MVD) at enrollment.
- Monitor consent rates for longitudinal EMR access and secondary data use.
- Identify gaps in baseline data completeness and develop strategies to mitigate missing information.
- Track participant retention at 12, 18, 24, and 36 months, and evaluate completion of at least three consecutive follow-ups.
- Identify early indicators of dropout or disengagement to inform retention strategies.
- Monitor response rates to quarterly PRO surveys (e.g., MPN-SAF TSS, PROMIS Short Form v1.0 – Fatigue 8a) and evaluate follow-up strategies (automated vs. manual).
- Assess the proportion of participants using secondary contacts (caregivers, clinicians) for follow-up.
- Measure success rates of EMR integration across sites using FHIR-based interoperability, compare self-reported and EMR-extracted data, and validate processing scalability.

Stage 2: Surrogate Endpoint Phase

- Establish composite surrogate endpoints integrating genetic markers (e.g., variant allele frequency shifts), clinical indicators (e.g., fibrosis progression, cytopenias), inflammatory markers (e.g., cytokine levels), and PROs (e.g., MPN-SAF TSS, PROMIS trends).
- Ensure surrogate endpoints align with FDA and EMA regulatory standards for clinical trials.
- Incorporate RWD (EMR, claims, PROs) to validate surrogate markers of disease progression.
- Determine time from baseline to first progression event (e.g., ET → PV → MF, blast phase transformation) and assess median time to progression by subtype.
- Measure progression rates per WHO 2022/IWG-MRT criteria using updated risk stratification models.

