5. PARTICIPATION CRITERIA

5.1 Inclusion Criteria

- Confirmed diagnosis of pre-PMF, primary MF, secondary MF, PV, ET, MPN-U, MPN-AP, MPN-BP or post-MPN AML, and MDS/MPN overlap syndrome as defined above per WHO 2022 criteria, including patients originally diagnosed with one of these conditions but who have received one or more SCTs and/or BMTs
- Willingness and ability to provide written informed consent.

- Willingness and ability to complete patient assessments, independently or with minimal assistance.
- Accessible EMR data from a participating healthcare institution to enable longitudinal data collection.
- U.S. residency, where the Registry has regulatory approvals and data-sharing agreements.
- Reasonable expectation of ongoing medical care and follow-up data availability for longitudinal objectives.

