5.2 Exclusion criteria

Participants will be excluded if they meet any of the following:

1. Lack of EMR data access due to technical limitations, non-participating institutions, or missing patient authorization (self-reported or claims-only data is insufficient for inclusion).
2. Missing compulsory data elements: WHO 2022 MPN diagnosis, date of initial diagnosis, or baseline demographics.
3. Lack of capacity to provide informed consent and absence of a legally authorized representative.
4. Significant gaps in clinical history, lab data, treatment records, or follow-up availability that limit longitudinal analysis.
5. Revised diagnosis to a non-MPN hematologic malignancy or other condition outside WHO 2022 criteria (other than post-MPN AML, and MDS/MPN overlap syndrome as defined above); such participants will be removed from future analyses.
6. Enrollment in external studies that restrict medical data access or impose data-sharing limitations incompatible with this Registry.

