6.3.1. Data Collection Intervals and Structured Follow-Up Schedule

Participants will be followed for a minimum of five years, with many continuing beyond ten years.

| Follow-Up | Data Collected | Collection Method |
|-----------|----------------|-------------------|
|-----------|----------------|-------------------|

| Timepoint | | |
|----------------------------|---|---|
| Baseline (Enrollment) | Demographics, medical history, WHO 2022 MPN subtype, other hematologic disease information (e.g., post-MPN AML, MDS/MPN overlap syndrome as defined above, history of SCT and/or BMT) baseline labs, molecular testing (if available), treatment history, and PROs (MPN-SAF TSS, EORTC QLQ-C30, modified PHQ-9, PGI-S, PROMIS Short Form v1.0 – Fatigue 8a) | Initial EMR extraction, PROs, insurance claims |
| Every 3 Months (0-10+ yrs) | Symptom burden updates (MPN-SAF TSS + PGI-S) | PROs |
| Every 6 Months (0-10+ yrs) | Updates on disease status, treatment changes, adverse events, healthcare utilization, molecular/genetics results (if available), mortality status, progression milestones, and PROs (MPN-SAF TSS, EORTC QLQ-C30, modified PHQ-9, PROMIS Short Form v1.0 – Fatigue 8a) | EMR reauthorization, PROs, claims retrieval, mortality data linkage |

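### Median time to first progression by subtype is timed from enrollment in a cohort entering at any disease duration, so it describes prognosis from registry entry and cannot be read unadjusted as natural history

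*Protocol*

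**What the plan says.** Under Stage 2, Section 4.1 asks the registry to "Determine time from baseline to first progression event" and, in the same bullet, to "assess median time to progression by subtype". No other time origin is given there. The follow-up table in Section 6.3.1 labels its first row "Baseline (Enrollment", so baseline is the date of joining the registry.

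Section 5.1 requires a "Confirmed diagnosis of pre-PMF, primary MF, secondary MF, PV, ET, MPN-U, MPN-AP, MPN-BP or post-MPN AML" or MDS/MPN overlap syndrome, "including patients originally diagnosed with one of these conditions but who have received one or more SCTs and/or BMTs". It puts no limit on time since diagnosis. The pre-screening questions in Section 10.6 ask for the diagnosis date and exclude nobody on the answer. The Background notes "Although some patients live decades post-diagnosis", so disease duration at entry may vary widely.

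Section 2 lists disease natural history among the registry's purposes, and Section 4.1 plans validation of endpoints against external registries. Section 3 describes the study as "designed to evaluate patients with MPNs using both historical and prospective data" but gives the historical data no role in setting a time origin. Section 5.2 excludes participants with "Missing compulsory data elements: WHO 2022 MPN diagnosis, date of initial diagnosis, or baseline demographics", and Section 7.1 collects duration of disease. Section 9.1 names time to progression and overall survival as primary endpoints without stating an origin.

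**The concern.** This is a prevalent cohort. A patient with ET who developed myelofibrosis before the registry reached them cannot contribute an ET progression; that patient enters as secondary MF. Those who died early do not enter at all. The participants observed in a given subtype are those who had not progressed by the time they joined, and the enrollment clock then measures only their remaining time.

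If the progression hazard changes with time since diagnosis, the remaining time depends on how long the patient had the disease at entry. Two subtypes with the same course could then show different medians only because one recruited longer-standing disease. The same holds for a comparison with an external cohort timed from diagnosis.

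A second issue concerns the word first. Under the criteria in Section 10.5, a secondary MF entrant has a documented earlier PV or ET, so the first event after baseline is not the first in that patient's disease. MPN-AP and MPN-BP entrants raise the same problem, because the objective itself counts blast transformation as progression.

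**Working it through.** **Plan's own figure.** The protocol states no median time to progression, no hazard shape and no distribution of disease duration at entry. There is nothing to reproduce, and what follows is illustration. Table 1 in Section 9 concerns detectable hazard ratios and does not bear on this point.

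**Assumptions (not from the documents).** Progression times from diagnosis follow a Weibull distribution with shape k and a true median of 15 years. Death and censoring are left out.

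**Step 1: entry at exactly d years.** The median remaining time r satisfies S(d + r)/S(d) = 1/2. For the Weibull this gives (d + r)^k = 15^k + d^k, so

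r = (15^k + d^k)^(1/k) − d.

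For k = 2:
- d = 5: √(225 + 25) − 5 = 15.8 − 5 = 10.8
- d = 10: √(225 + 100) − 10 = 18.0 − 10 = 8.0
- d = 15: √(225 + 225) − 15 = 21.2 − 15 = 6.2

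| Shape k | d = 0 | d = 5 | d = 10 | d = 15 |
|---|---|---|---|---|
| 0.7 (falling hazard) | 15.0 | 20.8 | 23.4 | 25.4 |
| 1 (constant) | 15.0 | 15.0 | 15.0 | 15.0 |
| 1.5 (rising) | 15.0 | 11.9 | 10.0 | 8.8 |
| 2 (rising) | 15.0 | 10.8 | 8.0 | 6.2 |

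The effect is absent under a constant hazard and its direction depends on the shape.

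**Step 2: a mixture of entry times.** A real cohort mixes durations, so single entry times exaggerate the contrast. A simulation drew 200,000 patients per scenario with entry uniform over 0–5, 0–10 or 0–20 years after diagnosis, and kept those free of progression at entry.

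| Shape k | Entry 0–5 | Entry 0–10 | Entry 0–20 |
|---|---|---|---|
| 1 | 14.9 | 15.0 | 15.0 |
| 1.5 | 13.3 | 12.2 | 11.0 |
| 2 | 12.8 | 11.2 | 9.4 |

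With entry over 0–20 years, the median from enrollment falls short of the true one by 15 − 11.0 = 4.0 years (shape 1.5) or 15 − 9.4 = 5.6 years (shape 2). For the same disease, a subtype recruited over 0–5 years and one recruited over 0–20 years would differ by 13.3 − 11.0 = 2.3 years (shape 1.5) or 12.8 − 9.4 = 3.4 years (shape 2).

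**Step 3: alternative analyses on the same simulated data.** Kaplan–Meier on time since diagnosis, with each patient entering the risk set at enrollment, returned 14.9 to 15.0 years in all nine scenarios. Timing from diagnosis without delayed entry returned 15.3 to 24.3 years, an overstatement throughout.

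**The case against.** Enrollment is a legitimate origin. The objective sits in the surrogate endpoint phase, PROs are first measured at enrollment, and prognosis forward from that date is a natural clock for marker work. It contains no immortal time. This stands, and it is why the enrollment clock should be kept.

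A reader might infer that the medians are simply wrong, or that they understate time to progression. The documents support neither. With a constant hazard there is no distortion, with a falling hazard the direction reverses, and the protocol gives nothing from which to choose among these.

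A reader might also infer from the use of historical data that follow-up before enrollment will be credited as time at risk. The text does not plan this: Section 4.1 says baseline, and Section 3 assigns the historical data no such role.

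It can further be said that time scales belong in the SAP, that adjustment for disease duration is not ruled out, and that no section says the subtype medians will be compared with diagnosis-timed medians. Silence on delayed entry in Section 9 is indeed no fault. But the objective itself sets the origin, and a SAP that follows it inherits the dependence on disease duration. With natural history a stated purpose and external validation planned, the interpretation should be fixed where the objective is written.

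**Conclusion.** The point holds in a limited form. As written, the subtype medians are medians from registry entry in a cohort of mixed disease duration that includes already progressed and transplanted patients. Unless the hazard is constant over time since diagnosis, they depend on the durations recruited. Without adjustment they should not be read as natural history, set against each other across subtypes, or compared with external cohorts timed from diagnosis.

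Size and direction are unknown. The figures of 11.0 to 9.4 years against a true 15 rest wholly on the assumed median, a Weibull shape of 1.5 to 2, and entry spread evenly over 0 to 20 years. The documents do not support replacing the time scale for every endpoint, overall survival included. Nor would time since initial diagnosis suit everyone: for secondary MF, MPN-AP, MPN-BP and post-transplant entrants it would mix in time from an earlier phase of disease.

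**What to change.** In Section 4.1:

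- Keep time from enrollment for prognosis and marker analyses, and label it as time from registry entry. Report it by subtype together with the distribution of disease duration at entry, stratified by or adjusted for that duration.
- For natural-history estimates and external comparisons, add an analysis on time since diagnosis of the subtype held at entry, which is the initial diagnosis for those who have not progressed. Participants enter the risk set at enrollment (left truncation), only progressions after enrollment count as events, and death is a competing event. The delayed entry is essential; moving the origin to diagnosis without it overstates the median.
- Report separately those entering with secondary MF, MPN-AP or MPN-BP, and those entering after transplant, because progression or transplant precedes their entry.

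The cost is mainly wording and one further analysis, with these downsides:

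- Risk sets soon after diagnosis will be sparse if few newly diagnosed patients join, which can make the curve unstable.
- Some diagnosis dates will be imprecise. Section 10.6 accepts a year alone or an unsure answer, and Section 7.2 strips dates other than year from stored data, so intervals should be derived before coding.
- Only the initial diagnosis date is compulsory; the date of the current subtype must be taken from the records.
- Delayed entry assumes that the time of joining is independent of prognosis. With enrollment through a portal this is not assured and should be stated as an assumption.

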4.2. Secondary Objectives

- **Characterize Disease Burden and Risk Stratification**
Develop a composite risk model distinguishing high- and low-risk patients by integrating genetic, inflammatory, and clinical markers. Assess how cytokine levels and inflammatory pathways influence disease trajectory and symptom burden.
- **Evaluate Treatment Response as a Surrogate for Disease Progression**
Compare progression rates in patients treated with JAK inhibitors, interferons, investigational agents, and other drugs. Determine whether therapy-induced molecular or clinical changes correlate with improved outcomes.
- **Analyze Genetic and Morphological Disease Evolution**
Monitor available variant allele frequency (VAF) changes in high-risk mutations and evaluate bone marrow fibrosis progression, where data is available, to understand clinical implications.
- **Assess Quality of Life and Symptom Burden at Disease Progression**
Track longitudinal changes using validated PROs, including MPN-SAF TSS, EORTC QLQ-C30, modified PHQ-9, PGI-S, and PROMIS Short Form v1.0 – Fatigue 8a, to evaluate how symptom burden correlates with disease progression

4.3. Exploratory Objectives

- **Develop Predictive Models for MPN Progression**
Train and validate artificial intelligence (AI) and machine learning (ML) models to predict time to disease progression, likelihood of transformation to accelerated or blast phase, and overall survival using early clinical and molecular indicators.
- **Validate Findings Across External Data Sources**
Compare registry data against European MPN registries, Mayo Clinic datasets, and claims-based registries to assess consistency, generalizability, and cross-cohort validation.
- **Assess Healthcare Utilization and Economic Impact**
Track hospitalization rates, transfusion needs, major interventions, and conduct cost-effectiveness analyses to inform early intervention strategies and support health policy development
- **Assess Early Patterns of Care and Treatment Setting Influence**
Evaluate how early patterns in healthcare utilization—including differences between academic centers, community hospitals, and rural clinics—impact disease monitoring, treatment choices, referral patterns, and long-term outcomes. Identify disparities in access to specialized care and examine how practice setting influences adherence to evidence-based guidelines and clinical outcomes.

5. PARTICIPATION CRITERIA

5.1 Inclusion Criteria

- Confirmed diagnosis of pre-PMF, primary MF, secondary MF, PV, ET, MPN-U, MPN-AP, MPN-BP or post-MPN AML, and MDS/MPN overlap syndrome as defined above per WHO 2022 criteria, including patients originally diagnosed with one of these conditions but who have received one or more SCTs and/or BMTs
- Willingness and ability to provide written informed consent.

- Willingness and ability to complete patient assessments, independently or with minimal assistance.
- Accessible EMR data from a participating healthcare institution to enable longitudinal data collection.
- U.S. residency, where the Registry has regulatory approvals and data-sharing agreements.
- Reasonable expectation of ongoing medical care and follow-up data availability for longitudinal objectives.

5.2 Exclusion criteria

Participants will be excluded if they meet any of the following:

1. Lack of EMR data access due to technical limitations, non-participating institutions, or missing patient authorization (self-reported or claims-only data is insufficient for inclusion).
2. Missing compulsory data elements: WHO 2022 MPN diagnosis, date of initial diagnosis, or baseline demographics.
3. Lack of capacity to provide informed consent and absence of a legally authorized representative.
4. Significant gaps in clinical history, lab data, treatment records, or follow-up availability that limit longitudinal analysis.
5. Revised diagnosis to a non-MPN hematologic malignancy or other condition outside WHO 2022 criteria (other than post-MPN AML, and MDS/MPN overlap syndrome as defined above); such participants will be removed from future analyses.
6. Enrollment in external studies that restrict medical data access or impose data-sharing limitations incompatible with this Registry.

6. PARTICIPANT RECRUITMENT AND ENROLLMENT

The MPN Research Foundation aims to enroll a representative cohort that reflects the heterogeneity of MPN biology across varied ancestral, socioeconomic, geographic, and clinical backgrounds. Recruitment strategies will include:

- Establishing partnerships with community health centers, primary care providers, and hematology/oncology clinics to broaden outreach.
- Utilizing targeted online advertising through search engines and social media platforms, patient advocacy networks, and Search Engine Optimization (SEO) to enhance visibility.
- Providing standardized educational toolkits to healthcare providers to promote referrals.
- Deploying patient navigators to engage potential participants via phone, email, or online platforms to address barriers.
- Offering multilingual, plain-language materials to improve accessibility and health literacy.
- Monitoring demographic heterogeneity in real time and adjusting strategies to improve representation of underrepresented populations.

6.1. Duration of Observation and Participation

Participants will be followed for a minimum of five years, with the potential for extended participation beyond ten years to support long-term observational analyses.

Standardized data collection will occur at baseline, six months, and every six months thereafter. Collected data will include:

- EMR extractions (clinical history, labs, imaging, treatments)
- Insurance claims and pharmacy records (healthcare utilization, medication use)
- PROs, including MPN- SAF TSS, PROMIS Short Form v1.0 – Fatigue 8a, and quality-of-life assessments

Data integration will prioritize FHIR-based EMR retrieval, supplemented by validated participant surveys and secondary data sources.

Ongoing monitoring and planned assessments include:

- **Year 1:** Baseline validation, data completeness review, and participant engagement check
- **Year 3:** Disease trajectory modeling, retention analysis, and interim outcome assessment
- **Year 5 and beyond:** Predictive analytics on disease progression, long-term outcomes, and composite endpoint evaluation

To promote retention, the Registry will deploy automated reminders, provide quarterly study updates, and offer virtual engagement opportunities (e.g., newsletters, webinars). Participants may withdraw at any time, as outlined in Section 6.2.

